1.2.3 Rationale for Endpoints

This study aims to establish whether the combination of pembrolizumab (MK-3475) and conventional cisplatin-based chemoradiotherapy is tolerable and results in acceptable levels of acute and late toxicity in patients with stage IV LA-SCCHN. In particular, the study will provide data on the levels of mucosal and cutaneous toxicity within the radiation fields, as these are the primary acute toxicities associated with this treatment regimen. In addition, toxicity outside the radiation portals (which may theoretically be exacerbated by radiation) will be studied. However, all toxicity will be monitored. This study will also give an indication of the activity of pembrolizumab in LA-SCCHN because we are deliberately selecting a group of patients with high- and intermediate-risk disease who have a significant chance of experiencing loco-regional or systemic failure.

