5.3 Clinical Procedures/Assessments

5.3.1 Adverse Event (AE) Monitoring

The investigator / designee will assess each patient for potential new or worsening AEs as specified in the schedule of study assessment (Table 2) and more frequently if clinically indicated. Adverse events will be graded and recorded from the first dose of pembrolizumab until the patients 12 weeks safety follow-up visit according to NCI CTCAE Version 4.0 (see Appendix 2). Toxicities will be characterized in terms regarding seriousness, causality, toxicity grading, and action taken with regard to trial treatment.

All AEs of unknown aetiology associated with pembrolizumab exposure should be evaluated to determine if it is possibly an event of clinical interest (ECI) of a potentially immunologic aetiology (irAE). See Section 7 and Appendix 5 regarding the identification, evaluation and management of AEs of a potential immunological aetiology. Please refer to section 7 for detailed information regarding the assessment and recording of AEs.

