Immune-related Adverse events (IrAEs) may be defined as an adverse event of unknown etiology, associated with drug exposure and is consistent with an immune phenomenon. irAEs may be predicted based on the nature of the pembrolizumab compound, its mechanism of action, and reported experience with immunotherapies that have a similar mechanism of action. Special attention should be paid to AEs that may be

suggestive of potential irAEs. An irAE can occur shortly after the first dose or several months after the last dose of treatment.

If an irAE is suspected, efforts should be made to rule out cancer, infectious, metabolic, toxin or other etiologic causes prior to labelling an adverse event as an irAE.

Recommendations to managing irAEs not detailed elsewhere in the protocol are detailed in the below table.

irAE	Withhold/Discontinue pembrolizumab?	Supportive Care
Grade 1	No action	Provide symptomatic treatment
Grade 2	May withhold pembrolizumab	Consider systemic corticosteroids in addition to appropriate symptomatic treatment. Based on limited data from clinical studies in subjects whose immune-related adverse reactions could not be controlled with corticosteroid use, administration of other systemic immunosuppressants can be considered.
Grade 3 and Grade 4	Withhold pembrolizumab Discontinue if unable to reduce corticosteroid dose to < 10 mg per day prednisone equivalent within 12 weeks of toxicity	Systemic corticosteroids are indicated in addition to appropriate symptomatic treatment. May utilize 1 to 2 mg/kg prednisone or equivalent per day. Steroid taper should be considered once symptoms improve to Grade 1 or less and tapered over at least 4 weeks. Based on limited data from clinical studies in subjects whose immune-related adverse reactions could not be controlled with corticosteroid use, administration of other systemic immunosuppressants can be considered.

Table 12: General Approach to Handling irAEs

Details for managing specific irAEs are summarised below:

Immune-mediated pneumonitis

Monitor patients for signs and symptoms of pneumonitis. If pneumonitis is suspected, evaluate with radiographic imaging. Exclude other causes of pneumonitis, and manage treatment in accordance with the guidelines above. Administer corticosteroids, withhold pembrolizumab for moderate (Grade 2) pneumonitis, and permanently discontinue pembrolizumab for severe (Grade 3) or life-threatening (Grade 4) pneumonitis.

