7.2 Assessing and Recording Adverse Events

All adverse events will be recorded from the first dose until the safety follow-up in the CRF. They will be followed up according to local practice until the event has stabilised or resolved, or the follow-up visit has taken place, whichever is the sooner. Serious Adverse Events (SAEs) will also be recorded throughout the study. The reporting timeframe for adverse events meeting any serious criteria is described in section.

Follow-up of AEs with a causality of possible, probable or highly probable will continue until the events resolve, stabilise or the patient completes the trial. Any unresolved AEs at the patient's last visit should be followed up for as long as medically indicated, but without further recording in the CRF.

If an Investigator learns of any AE that he/she consider serious, including death, at any time after a patient has completed the study and he/she considers there is a reasonable possibility that the event is related to pembrolizumab, the Investigator should notify the RM-CTU.

The following details will be collected in the CRF for each AE:

- AE description / diagnosis
- Date of onset and date of resolution
- NCI-CTCAE grade maximum intensity
- Seriousness
- Investigator causality rating against the study medication (yes or no)
- Action taken with regard to study medication
- Outcome

For the pre-registration period adverse events will not be collected in patients that have not undergone any protocol-specified procedure or intervention. If the patient requires a blood draw, fresh tumour biopsy etc. for the study then the patient will be required to consent to the main study and AEs will be captured as described above.

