8.0 STATISTICAL ANALYSIS PLAN

8.1 Statistical Analysis Plan Summary

8.2 Endpoints

8.2.1 Primary Endpoint

A: To establish the maximum tolerated dose that can safely be combined with platin-based chemoradiotherapy in patients with HPV-ve and with HPV+ve LA-SCCHN, respectively.

B: To evaluate acute toxicity in each HPV group as measured during treatment by CTCAE v4.0.

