8.2.5 Data analysis

All quantitative data will be presented as number of observations, means and SDs for normally distributed data or as median and interquartile ranges for data that appear to be non-normally distributed. Qualitative data will be presented as number of observations and frequencies. When appropriate, data will be presented together with 95% confidence intervals. All statistical tests will be two-tailed and a p-value <0.05 (5%) will be considered as achieving statistical significance. The analysis will be performed separately in HPV-ve and HPV+ve cohorts, respectively.

- Baseline characteristics will be summarized using descriptive statistics. Dose limiting toxicity will be summarized using overall frequencies. Incidence (highest grade) of side effects of radiotherapy (CTCAE scale v 4.0, for acute side effects and LENT SOMA for late radiotherapy scoring systems) will be reported.
- Duration of clinical benefit will be calculated as the number of patients who had a best overall response of CR, PR, or SD according to the RECIST criteria until the first date of recurrence or progressive disease (PD) and will be measured at the landmark points in the study **6 months, 1 year and 2 years, respectively**. They will be presented as proportions and 95% confidence intervals will be reported if appropriate.
- Progression free and overall survival will be determined using Kaplan-Meier methods **presenting the median survival times, and survival rates will be reported at 6 months, 1 and 2 years, respectively**. Overall survival will be measured from date of treatment to date of death from any cause; surviving patients will be censored at date last known to be alive. Progression free survival will be measured from start of treatment to date of first appearance of disease progression, relapse or death from any cause. Patients alive without progression or relapse will be censored at date last known to be alive. Survival curves will be estimated for each HPV cohort and compared using the log-rank test.

- The levels of CD4, CD8, T regulatory cell (CD4/CD25, FOXP3), B cells, NK cells and Circulating free tumour DNA pre RT, during RT and post RT will be presented as descriptive statistics according to their HPV status. The expression of PD1 (and other immune exhaustion markers) on immune cells and PDL1 on tumour cells will be presented as descriptive statistics.

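### Apart from DLT frequencies, the only adverse-event summary named in section 8.2.5 is of radiotherapy side effects, which is narrower than primary endpoint B, and the endpoint's window is undefined

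*Combined protocol and SAP*

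**What the plan says.** The SAP is section 8 of the protocol, and its analysis rules are in 8.2.5. Two sentences there deal with toxicity. The first reads "Dose limiting toxicity will be summarized using overall frequencies". The second calls for reporting of "Incidence (highest grade) of side effects of radiotherapy (CTCAE scale v 4.0, for acute side effects", with LENT SOMA for late radiotherapy effects. A general rule says that qualitative data are shown as counts and frequencies, separately by HPV cohort. No table is named for all adverse events, pembrolizumab-related events, immune-related events, events of clinical interest (ECIs) or serious adverse events (SAEs).

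Primary endpoint B in 8.2.1 is broader: "To evaluate acute toxicity in each HPV group as measured during treatment by CTCAE v4.0". The rationale in 1.2.3 also says that "toxicity outside the radiation portals (which may theoretically be exacerbated by radiation) will be studied". Section 4.4 describes the primary endpoint as treatment-related toxicity.

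On collection, 5.3.1 states: "Adverse events will be graded and recorded from the first dose of pembrolizumab until the patients 12 weeks safety follow-up visit". The adverse-event form described in 7.2 includes "Investigator causality rating against the study medication (yes or no"). It lists no corresponding field for radiotherapy or platin.

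**The concern.** This is a phase I safety trial in which pembrolizumab is the added, untested component and chemoradiotherapy is the known one. The only grade-by-grade summary that could serve endpoint B is worded around the known component. A statistician who followed 8.2.5 to the letter would report mucositis and skin reactions. A Grade 2 pneumonitis, a Grade 2 infusion reaction or a platin-related renal event would be left out unless it was a DLT. Any table of those events would then be chosen after the data were seen.

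The time window adds to this. Endpoint B ends with treatment, but section 6.6 warns that "An irAE can occur shortly after the first dose or several months after the last dose of treatment". The late endpoint in 8.2.2 uses LENT SOMA and concerns radiotherapy only. A CTCAE immune event between the end of treatment and the safety follow-up therefore belongs to no endpoint.

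**Working it through.** No figure in the plan is in dispute. The sample size in 8.2.4 reproduces and is unaffected: minimum 3 × 2 cohorts = 6; maximum (2 levels × 6 + 6 expansion) × 2 cohorts = 36.

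**Scope, section against section**

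| Section | Toxicity in scope |
|---|---|
| 2.1.1 primary objective | Safety of chemoradiotherapy combined with pembrolizumab |
| 1.2.3 | In-field and out-of-field toxicity; all toxicity monitored |
| 1.2.3.1 | CTCAE toxicity used to judge the combination |
| 4.4 | Treatment-related toxicity |
| 2.2.1 and 8.2.1, endpoint B | Acute CTCAE toxicity, no restriction by cause |
| 8.2.5, summary by grade | Radiotherapy side effects |

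The last row is narrower than every row above it.

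**What the DLT summary adds.** Section 3.3 counts listed haematological events, severe mucositis, toxicity-related delay of more than 2 weeks, and other non-haematological toxicity of Grade 3 or higher that the investigator considers dose-limiting. Pembrolizumab and platin toxicity can enter by these routes. A Grade 2 pneumonitis is an ECI in Table 13 and leads to withholding under Table 10, but it is not a DLT unless it causes a delay of more than 2 weeks.

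**Timeline with no delays** (3.2, 3.3, 3.5.4 and Table 2), taking cycle 1 as week 0:

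- Pre-loading dose: week −2.
- End of radiotherapy: week 7.
- DLT window closes: 7 + 6 = week 13.
- Cycles 6 and 7: weeks 15 and 18.
- Safety follow-up: 18 + 12 = week 30.
- Adverse-event collection: 30 − (−2) = 32 weeks.

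**DLT window.** Counted from the pre-loading dose it is 13 − (−2) = 15 weeks, and 15/32 = 47%. The remaining 17 weeks (53%), including two of the eight pembrolizumab doses, lie outside it.

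**Endpoint B window.** The treatment period is not defined, so the share of collection time outside it depends on the reading:

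- Treatment ends at the last infusion (week 18): (30 − 18)/32 = 12/32 = 37.5%.
- Cycle 7 runs its full 3 weeks (week 21): (30 − 21)/32 = 9/32 = 28%.
- Radiotherapy period only (weeks 0 to 7): 7/32 = 22% is inside, so 25/32 = 78% is outside.

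For a patient whose last dose is cycle 4 (week 9), collection runs from week −2 to week 21, or 23 weeks. The share outside is 12/23 = 52% on the last-infusion reading and 9/23 = 39% on the full-cycle reading.

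**The case against.** The strongest reply is that 8.2.5 contains one loose phrase and not a decision to leave out drug toxicity. Endpoint B is unrestricted, 1.2.3 says all toxicity will be monitored, and the general rule on qualitative data would permit full adverse-event tables. The data are collected, the endpoint is descriptive, and the safety review committee sees all SAEs and emerging safety data (10.8.2). Much of this stands: nothing is lost beyond recovery, and the intent elsewhere is clear. But the general rule names no adverse-event category, committee review is oversight and not a planned analysis, and the one specific rule points to radiotherapy.

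Four stronger readings are tempting and are not supported:

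- **That the radiotherapy summary is the only toxicity analysis.** DLT frequencies are a second one and can capture pembrolizumab and platin toxicity up to about week 13.
- **That the 8.2.5 analysis is itself confined to the treatment period.** That limit is in the definition of endpoint B. The 8.2.5 sentence has no window and extends to late LENT SOMA effects.
- **That the rule cannot be applied because causality is rated only against the study medication.** In-field reactions can be picked out by CTCAE term, and 5.3.2 provides a separate radiotherapy toxicity assessment. The fair criticism is that no list of terms is given.
- **That the omitted events decide whether 200 mg goes to phase 2.** Under 3.1 and 3.3 that rests on DLT counts.

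**Conclusion.** The concern holds as an inconsistency between the analysis rule and the primary endpoint. Apart from DLT frequencies, 8.2.5 names only radiotherapy side effects, so immune-related, infusion-related and platin toxicity short of a DLT has no planned summary.

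Separately, endpoint B is limited to an undefined treatment period. With no delays, 28% to 37.5% of collection time falls outside it if treatment ends between week 21 and week 18; for early stoppers the share is larger. These are shares of calendar time, not of events, and the documents give no basis for estimating how many events would fall there.

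It should be fixed because it concerns a primary endpoint of a safety trial and the remedy is cheap. It is not critical: escalation, MTD determination and sample size do not depend on it.

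**What to change.** Replace the adverse-event sentence in 8.2.5 with the highest-grade incidence of all CTCAE v4.0 adverse events regardless of attribution, from the first pembrolizumab dose to the 12-week safety follow-up. Count each patient once per term at worst grade, and present results by HPV cohort and dose level. Add tables of pembrolizumab-related events, SAEs, and immune-related events and ECIs as defined in Table 13. Show in-field radiotherapy reactions as a subset with its terms listed in advance, and keep LENT SOMA for late effects. In 2.2.1 and 8.2.1, replace the undefined treatment period in endpoint B with the same collection window.

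The cost is a few more tables, mainly from data already collected. One limit should be stated: 6.4.2 largely stops recording concomitant medication 30 days after the last dose, so Table 13 criteria that turn on steroid use cannot be applied in full after that. Changing the endpoint wording needs a protocol amendment with sponsor and ethics review (9.2.2); because the SAP is part of the protocol, one amendment can carry both changes. Reported toxicity rates will look less favourable, since more events are counted. The DLT definition, the escalation and MTD rules, and the sample size stay as they are.

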5.3.9.3 Timing and Assessment of Disease

Tumour imaging may be performed by CT or magnetic resonance imaging (MRI), but the same imaging technique should be used in a patient throughout the trial. The initial tumour imaging will be performed no more than 28 days prior to confirmation of eligibility. Scans performed as part of routine clinical management are acceptable for use as the screening scan if they are of diagnostic quality and performed within the correct time window.

On-study imaging will be performed at screening then at cycle 6 to assess disease response. After cycle 6 imaging will be performed every 12 weeks for 12 months and should follow calendar days and should not be adjusted for delays in cycle starts or extension of pembrolizumab cycle frequencies.

Local investigator assessment with site radiology will be used to determine eligibility and for patient management. Tumour imaging and assessment per local standard of care should be performed for patient management, and may include additional imaging (e.g. bone scan for lung cancer patients).

Imaging should continue to be performed until documented disease progression, the start of new anti-cancer treatment, withdrawal of consent, death, or the end of the study, whichever occurs first.

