8.2.2 Secondary Endpoints

1. To measure the PFS and overall survival at 6 months, 1 year and 2 years, respectively.
2. To measure the duration of clinical benefit using RECIST at 6 months, 1 year and 2 years, respectively.
3. To evaluate late radiotherapy toxicities as measured during treatment by LENT SOMA 52 weeks from the end of radiation therapy (week 7).

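### Section 8.2.5 computes duration of clinical benefit as a count of patients, leaves out death, and sets no time origin, denominator or censoring rule, so the secondary endpoint does not measure a duration

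*Combined protocol and SAP*

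**What the plan says.** Section 8.2.2 of the combined protocol and SAP names the endpoint as a duration: "To measure the duration of clinical benefit using RECIST at 6 months, 1 year and 2 years, respectively". Section 2.2.2 lists the same endpoint, and section 2.1.2 makes the duration of SD, PR or CR a secondary objective.

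The calculation appears only in section 8.2.5. It reads "Duration of clinical benefit will be calculated as the number of patients who had a best overall response of CR, PR, or SD" by RECIST, "until the first date of recurrence or progressive disease (PD) and will be measured at the landmark points in the study". On reporting it says: "They will be presented as proportions and 95% confidence intervals will be reported if appropriate".

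The next bullet of 8.2.5 treats the other secondary time endpoints differently: "Progression free and overall survival will be determined using Kaplan-Meier methods". There the origin, the events and the censoring are all written down: "Progression free survival will be measured from start of treatment to date of first appearance of disease progression, relapse or death from any cause", and "Patients alive without progression or relapse will be censored at date last known to be alive".

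On follow-up, section 5.3.9.3 says: "After cycle 6 imaging will be performed every 12 weeks for 12 months". Sections 3.5.5 and 3.5.6 end disease-status visits 9 months after the 12-week safety visit. Section 8.2.6 sets the secondary analysis 1 year after the last patient is enrolled.

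**The concern.** The objective asks how long benefit lasts, and a count of patients cannot answer that. The reference to a first date of recurrence or PD shows that a time was intended, but no median or other summary of time is planned.

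Two gaps affect the numbers that will be reported. First, death is not an end event, so on a literal reading a patient who dies without documented progression never leaves benefit. Second, nothing says how to treat patients whose status at a landmark is unknown. They may be lost, have started new therapy and moved to telephone survival follow-up, or not yet have reached the landmark. Two analysts following 8.2.5 faithfully could publish different values from the same data.

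**Working it through.** **1. The plan's own figure.** The SAP's only computed figure is the sample size (8.2.4). Minimum 2 × 3 = 6; maximum 2 × (2 × 6 + 6) = 36, or 18 per HPV cohort. Both reproduce. No precision is stated for this endpoint.

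**2. The two definitions in 8.2.5 side by side.**

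| Element | Duration of clinical benefit | PFS |
|---|---|---|
| Time origin | none | start of treatment |
| End event | recurrence or PD | progression, relapse or death |
| Censoring | none | stated |
| Summary | proportions, no denominator | Kaplan-Meier, median and landmark rates |

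**3. Follow-up clock, counted from the pre-loading dose (2 weeks before cycle 1).**
- Last dose: week 18 + 2 = 20. Safety visit: 20 + 12 = 32. End of disease-status visits: 32 + 39 = week 71, and 71 × 7 / 30.44 = 16.3 months.
- Scans: cycle 6 at week 15 + 2 = 17, then weeks 29, 41, 53 and 65 (15.0 months).
- Accrual inferred from the Trial Summary: 30 months total less 15 to 18 months' participation = 12 to 15 months. At the analysis, the share enrolled at least 24 months earlier is (24 − 24)/12 = 0% to (27 − 24)/15 = 20%, or 3.6 of 18.

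**4. Effect of the counting rule at 1 year.** These assumptions are not in the documents: constant hazard, true 1-year benefit S of 60, 70 or 80%, 10% loss per year, and 0 to 20% of events being death without PD (share d).

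With λ = −ln S and μ = −ln 0.9 per year, the probability that an event is observed by 1 year is P = λ/(λ + μ) × (1 − 0.9 S). For S = 0.70: 0.3567/0.4620 × (1 − 0.63) = 0.286.
- (a) No recorded PD counts as benefit, all patients in the denominator: 1 − (1 − d)P.
- (b) Only patients seen in benefit count, all patients in the denominator: 0.9 S.
- (c) Known status only: 0.9 S/(0.9 S + P).

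| True S | (a) d = 0% | (a) d = 20% | (b) | (c) |
|---|---|---|---|---|
| 60% | 62% | 70% | 54% | 59% |
| 70% | 71% | 77% | 63% | 69% |
| 80% | 81% | 85% | 72% | 79% |

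The error runs from about −8 points (rule b, S = 80%) to about +10 points (rule a, S = 60%, d = 20%). Rule (c) is within about 1 point. Moving d from 0% to 20% adds 4 to 8 points under rule (a). A simulation of 400,000 patients agrees with these values.

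**5. Two years.** True values are 0.60², 0.70² and 0.80² = 36, 49 and 64%. In the simulation rule (a) is 12 to 28 points too high, and rules (b) and (c) give 0%, because nobody is assessed at 24 months.

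**6. Does Kaplan-Meier repair it?** In 4,000 simulated cohorts of 18, with death as an event and timing from first dose, the mean 1-year estimates were 0.60, 0.70 and 0.80, with standard errors of about 0.10 to 0.12 and about 10 to 13 at risk. At 2 years nobody was at risk. The curve carried forward reads S^(16.3/12) = 0.50, 0.62 and 0.74 against true 0.36, 0.49 and 0.64. The cause at 2 years is therefore the follow-up schedule, not the choice of estimator.

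**The case against.** The strongest reply is that the bullet is loosely worded but can be read as a landmark benefit rate. PFS next to it already reports time to progression or death by Kaplan-Meier at the same landmarks, so little information is lost. The endpoint is descriptive, has no test attached, and affects neither the MTD nor the sample size. With at most 18 per cohort, sampling error is larger than the 1-year error: the exact 95% interval for 13/18 is 47% to 90%.

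Most of that stands, and it limits the importance of the point. It does not remove it. A landmark rate still needs a denominator and a rule for deaths and unknown status, and the endpoint and its objective are both named as durations.

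Three stronger readings are tempting, and the documents do not support them:
- *That the landmarks are shown to be biased upwards.* The text fixes no counting rule, so the direction is not determined.
- *That unobserved patients must be scored as benefit or failure.* They can be excluded, which is nearly unbiased at 1 year under the assumptions used here.
- *That the large 2-year error comes from using proportions instead of Kaplan-Meier.* It comes from disease follow-up ending at about 16.3 months and from the analysis date. 2-year PFS has the same difficulty although it uses Kaplan-Meier.

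Section 5.3.9.3 also lets imaging run to the end of the study. If that overrides the 12-month limit, at most about 20% of patients could have 2-year data at the planned analysis.

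**Conclusion.** The point holds as a defect of definition in a secondary endpoint and should be corrected. Section 8.2.5 as written yields no duration, omits death, and leaves the landmark values to an unstated convention. These findings rest on the text alone.

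The sizes rest on the assumptions in step 4 of the working. At 1 year the error is modest, and it can be negligible under a sensible rule. At 2 years no estimator gives a usable value under the scheduled follow-up and analysis date, and this is a separate problem from the definition.

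**What to change.** Amend 8.2.5 as follows.
- **Population and time.** Among patients with best response CR, PR or SD, measure from the first assessment documenting CR, PR or SD to first PD, recurrence or death from any cause. Use this single origin. The first on-study scan is at cycle 6, so timing a group selected on that response from start of treatment would credit them with about 17 weeks in which they could not fail (guarantee time).
- **Censoring.** Censor at the last disease assessment, stating whether clinical visits count as well as scans. Do not copy the PFS rule of last known alive, because some patients are followed for survival only.
- **Estimation.** Use Kaplan-Meier within each HPV cohort, with the median, landmark estimates, 95% confidence intervals and numbers at risk.
- **Response rates.** Report CR, PR and SD separately as proportions of treated patients.
- **Two years.** State in 2.2.2, 8.2.2 and 8.2.5 that the 2-year estimate is reported only if patients remain at risk and is otherwise not estimable.

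The cost is wording only. The dates needed are collected up to the end of scheduled disease follow-up, but not at 24 months.

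There are three downsides. Cohorts of at most 18 give wide intervals. The result overlaps with PFS. The later origin also shortens follow-up: from a week-17 scan, visits run 71 − 17 = 54 weeks and scans 65 − 17 = 48 weeks, and the last patient enrolled has about 52 − 17 = 35 weeks at analysis. The 1-year estimate from this origin will therefore be thin, and the at-risk condition should apply to it too.

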1.0 BACKGROUND & RATIONALE

1.1 Background

Stage III-IV locoregionally advanced squamous cell cancer of the head and neck (LA-SCCHN) accounts for over 50% of patients diagnosed with head and neck cancer [1]. Following radical non-surgical treatment, five-year overall survival (OS) rates for LA-SCCHN vary from 10% to 75% depending on tumour stage, the site of the primary tumour, the association with human papillomavirus (HPV) and other known risk factors [2]–[6]. For oropharyngeal squamous cell carcinoma, specific risk groups have been clearly defined: high-risk patients are those with locally advanced disease, with HPV-negative tumours who either have a ≤ 10 pack-year smoking history with T4 tumours or have a >10 pack-year smoking history irrespective of T stage [7], [8]. Patients with HPV-positive tumours and a >10 pack-year smoking history also have a worse prognosis and are defined as being at an intermediate risk of death. Overall survival (OS) in patients with high-risk locally advanced oropharynx cancer is low (3-year OS 46.2% following concurrent chemoradiotherapy (CRT)), compared with 70.8% in the intermediate-risk and 93% in the low-risk groups [7]. Locally advanced laryngeal and hypopharyngeal cancers behave as high- to intermediate-risk tumours. Both locoregional failure and systemic metastatic relapse represent major causes of disease persistence/recurrence and account for significant morbidity and mortality in high-risk disease. In patients with intermediate-risk disease, systemic metastasis represents a particular problem [9]. Meta-analysis data have failed to show a role for adjuvant chemotherapy as a means of reducing the risk of locoregional or systemic failure in LA-SCCHN [10]. Therefore, there is a significant unmet need for novel therapies to improve outcomes in patients with high- and intermediate-risk disease and, currently, the only ongoing studies involve small molecule inhibitors of c-erbB signalling pathways. Data presented in abstract form at ASCO 2014 have recently shown that use of the EGFR/HER2 dual tyrosine kinase inhibitor, lapatinib, during and after post-operative adjuvant cisplatin-based chemoradiotherapy is not associated with improved progression-free or overall survival [11].

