3.5.7 Survival Follow-up – Patients who have disease progression

Once a patient experiences confirmed disease progression or starts a new anti-cancer therapy, the patient moves into the survival follow-up phase and should be contacted by telephone every 12 weeks to assess for survival status until death, withdrawal of consent, or the end of the study, whichever occurs first. If a patient progresses on treatment they will also be required to attend a SFU at 12 weeks or before the initiation of a new anti-cancer treatment; whichever comes first.

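### Overall survival is biased downward after about 16 months, because only patients who progress or start new therapy are followed for survival beyond that point

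*Combined protocol and SAP*

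**What the plan says.** Section 8.2.5 specifies Kaplan-Meier estimates for progression-free and overall survival, "presenting the median survival times" together with the rates at 6 months, 1 year and 2 years. For OS, "surviving patients will be censored at date last known to be alive". The cohorts are then contrasted: "Survival curves will be estimated for each HPV cohort and compared using the log-rank test". No common data cut-off is given, and no condition on maturity before a median is quoted.

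Follow-up depends on progression status. Sections 3.5.5 and 3.5.6 see patients without progression, whether they completed or stopped pembrolizumab, for 9 months after the 12-week safety visit. Neither section provides later contact. Section 3.5.7 covers patients who progress or start a new anti-cancer therapy; they "should be contacted by telephone every 12 weeks to assess for survival status until death", withdrawal of consent or end of study. Section 3.6 ends the study when the last patient finishes post-safety follow-up. Section 8.2.6 places the secondary analysis one year after the last enrolment.

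Section 1.1 gives 3-year OS of 46.2% for high-risk oropharynx cancer, "compared with 70.8% in the intermediate-risk and 93% in the low-risk groups". The documents state no median OS.

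**The concern.** Kaplan-Meier assumes that patients censored at a given time have the same outlook as those still followed. Here the follow-up rules break that assumption. Beyond about 16 months the patients doing well leave the risk set, and those who have progressed or needed new therapy stay in it. Deaths in this poor-prognosis remainder are then read as the death rate of the whole cohort.

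The stake is a declared secondary endpoint, 2-year OS, together with any median and the comparison of HPV cohorts. Section 3.1 sends the regimen on to a randomised phase 2 study, so these figures will be read as the first survival signal for the combination. Progression-free survival is not affected by this mechanism, because contact after progression does not enter it.

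**Working it through.** **1. When contact ends.** The pre-loading dose is 2 weeks before cycle 1 and cycle 7 is at week 18 (section 3.2, Table 2), so the last dose is 20 weeks after the first. Adding 12 weeks to the safety visit gives 32 weeks = 7.4 months; adding 9 months gives 16.4 months. This agrees with the 15-18 months of participation in the trial summary. A patient who stops after one dose without progression leaves at 12 weeks + 9 months = 11.8 months.

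**2. Longest follow-up at the analysis.** The summary gives a 30-month trial. Inferred accrual is 30 - 16.4 = 13.6 months. With analysis 12 months after the last enrolment, the longest possible follow-up is 13.6 + 12 = 25.6 months.

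**3. What the background figures imply.** With a constant hazard, median = 36 × ln 2 / (-ln S36).
- 46.2%: 36 × 0.693 / 0.772 = 32.3 months.
- 70.8%: 36 × 0.693 / 0.345 = 72.3 months.

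The first is fairly secure, because OS at 36 months is already just below 50%. The second is an extrapolation to twice the data horizon; without a model it says only that the median lies beyond 36 months.

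**4. Size of the bias in a very large cohort.** Assume exponential progression (rate a), then exponential death (rate b = ln 2 / m, where m is median survival after progression). Then S(t) = [b·exp(-at) - a·exp(-bt)] / (b - a), with a solved so that S(36) equals 0.462 or 0.708. Under the plan everyone at risk after 16.4 months has progressed, so the estimated curve is S(16.4) × exp[-b(t - 16.4)].

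Worked for m = 9 months (b = 0.0770):

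| Cohort | a | S(16.4) | × exp(-b × 7.6) | Estimated 24-month OS | True S(24) |
|---|---|---|---|---|---|
| HPV-ve | 0.0357 | 0.794 | 0.557 | 44% | 66% |
| HPV+ve | 0.0150 | 0.903 | 0.557 | 50% | 83% |

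With m = 6 and m = 12 the formula gives 32% and 52% (HPV-ve) and 37% and 59% (HPV+ve). Simulation gave about 33-51% and 37-58%, the same to within about a point. True values across m = 6 to 12 are 64-66% and 82-83%.

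The cohort contrast is also compressed. At m = 9 the true gap is 83 - 66 = 17 points and the estimated gap is 50 - 44 = 6 points, if survival after progression is the same in both cohorts.

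**5. Chance that a median OS is reported.** Simulation of the same model with 18 per cohort, uniform accrual over about 14 months, and the planned analysis time:

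| Cohort | Planned follow-up | Everyone followed to the cut-off |
|---|---|---|
| HPV-ve | 37-45% | 17-18% |
| HPV+ve | 24-27% | 3-4% |

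An independent run that allowed death without progression and m of 6 to 18 months gave 34-47% and 23-30% under the plan, against 21-24% and 4-5% with equal follow-up. When a median is reached, it is typically about 19 months under the plan and about 21-23 months with equal follow-up.

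**The case against.** A reader might infer that the plan will often print a false median of about 19 months where the truth is 32 or 72, and so make the combination look harmful. The documents do not support that reading.

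- Not reached is the likeliest result in both cohorts.
- Most of the distance from 19 months to 33 or 60 (the model's true medians) comes from short follow-up. Nobody has more than about 26 months at the analysis, so any median reached must lie below that even with equal follow-up. Unequal follow-up shortens a reached median by only about 2 to 4 months; its main effects are on how often a median appears and on the 24-month rate.
- The 3-year figures describe oropharynx risk groups, used here as proxies for the HPV cohorts, and entry is not limited to oropharynx. Section 1.1 also says that 5-year OS "rates for LA-SCCHN vary from 10% to 75% depending on tumour stage" and other factors. As exponential medians these are 60 × ln 2 / (-ln 0.10) = 18 months and 60 × ln 2 / (-ln 0.75) = 145 months. At the poor end, a median near 19 months would not be false.
- This is a phase I trial with a safety endpoint, no planned historical comparison of OS, and a randomised study to follow.

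Two further points bear on size. The date last known alive need not be a trial visit, and a single site may know more. If later status were known for half of the progression-free patients, the chance of a reported median falls to about 26% (HPV-ve) and 9% (HPV+ve); at 80% it is 19% and 5%. The documents neither promise nor exclude this. Accrual in a 3+3 design is also staggered rather than uniform: a staggered 12 per cohort gives about 25-27% and 13%, and a staggered 18 gives 54-59% and 38-39%.

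These points limit the claim about the median. They do not remove the gap in follow-up, which no other section closes.

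**Conclusion.** The concern holds as a follow-up and censoring problem. As planned, the OS risk set beyond about 16 months consists almost only of patients who progressed or started new therapy. Kaplan-Meier OS after that point is then biased downward, which affects the 2-year rate, any median and the late part of the log-rank test. The clearest measure is the large-cohort 24-month rate in step 4: too low by roughly 15 to 30 percentage points in HPV-ve and 25 to 45 in HPV+ve.

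The sizes assume post-progression medians of 6 to 12 months, calibration to 46.2% and 70.8% at 3 years, about 14 months of accrual, and no status information on progression-free patients after 16.4 months. Better ascertainment shrinks the bias and could nearly remove it. Within these assumptions the size varies, but the direction does not. A median understated because follow-up is short is a separate matter, which equal follow-up does not cure.

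**What to change.** In section 3.5, add a vital-status check for every patient, whatever their progression status, at one common data cut-off. In section 8.2.5, censor survivors at that date and then:

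- Report a median OS only if it is reached within this complete follow-up; otherwise state that it was not reached.
- Keep the 6-, 12- and 24-month rates with 95% confidence intervals and numbers at risk. Give the 24-month rate only where follow-up to 24 months is complete under this rule.
- Base the log-rank comparison on the same cut-off.

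This removes the bias but not the imprecision. At the planned analysis time, only patients enrolled in the first 25.6 - 24 = 1.6 months of accrual could have 24 months of follow-up. A well-supported 2-year rate therefore needs a later cut-off.

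If common cut-off status is not collected, restrict OS estimates to about 12 months, where follow-up is nearly alike (a patient who stops after one dose leaves at 11.8 months). State openly that the declared 2-year OS endpoint is then lost.

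The cost is one status check per patient, at most 36, at a single site, plus the protocol and SAP wording. Treatment and eligibility are unchanged.
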